### 11.2 Determination of Sample Size

A literature search about this tested topic does not provide enough strong references to build a confirmatory analysis. It seems that results might be strongly influenced by the inclusion criteria (first time vs experienced hearing aid users) or test design (cross-over, multi-investigator, or between group designs). There is no article to our knowledge that includes a multi-investigator effect in the test design when looking at the effect of different fitting procedures. Adding a -by investigator- treatment interaction term seems to be mandatory if this trial wants to be determine the effect that different investigators have on the fitting procedure.

The sample size cannot be computed on reported effect sizes from previous experiment; however, the following summary shall be used as an indication to determine the sample size for participants per investigator:

•Naylor et al. (2015) about the narrative effect during the fitting with 24 experienced users and 16 first time users,

•Humes et al. (2017) about the performance with over-the-counter hearing aids compared to audiology best practice with 154 participants,

•Dawes et al. (2013) about the placebo effect in hearing aid trials with 16 experienced hearing aid users,

•Dawes et al. (2011) about the placebo effect in hearing aid trials with 20 experienced hearing aid users.

A placebo effect was found with sample sizes of about 20 participants in a single site study design. Adding an investigator effect in the design might bring new insights in this domain but requires a minimum number of participants per investigator to reduce imbalance between them.

With an effect size of 0.65 from the literature review, 2 degrees of freedom, 24 participants, and an alpha of 0.05, we can achieve a power of 0.82. Therefore, a minimum of 24 participants will be included in the trial overall. There will be 4 investigators with 6 to 8 participants per investigator.

### 11.3 Statis tical criteria of termination of trial

A single statistical analysis is planned once all recruited subjects have completed the protocol (perprotocol). No interim analysis is planned for a test period of 14 days and no "stopping rules" are set from a statistical perspective. PI's and clinician judgement are considered as reliable enough to stop the trial.

### 11.4 Planned Analyses

The analysis and documentation will be done by the statistician using R (latest available and validated version) downloaded from the official Comprehensive R Archive Network (https://cran.r-project.org/). R-Studio IDE will be used to integrate the analysis to the report. R provides adequate packages for descriptive statistics (base, stats, and Rmisc), data visualisation (ggplot2), mixed effect models (Imer, ImerTest, and nIme), and principal component analysis (FactoMineR).

A linear mixed effect regression will be used on the IOI-HA questionnaire, chi-squared distribution on the preference test and a paired t-test on hearing thresholds. The principal component analysis will be made on different outcomes and explanatory variables combinations.

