Bernafon AG will carry out studies of the IMD with test participants who have hearing loss in order to validate the performance and to qualify the benefit for the user when both the RMD and the IMD are used. Additionally, the results of the trial will be used to identify areas of further optimization of the tested products. The aim is to determine whether there is a narrative effect on the perceived benefit of the hearing aids from the RMD. Audiometry will be compared to ensure that similar results are achieved with the IMD as those from a standard audiometry test. Speech intelligibility will measure the objective benefit of the hearing aids. The trial will also provide safety information.

All participants are hearing impaired persons that have never used hearing aids before. They will be fit with hearing aids that have been on the market for 2 years, Juna 7 Nano BTEs. They will be fit two times during the trial, once with the RMD and once with the IMD.

The RMD is the standard first fit process of the Oasis software. The hearing thresholds are entered into the software and then used by the software to calculate the amount of amplification needed. The software has default settings for features such as noise reduction and directionality. The HCP saves the fitting and all settings are saved in the hearing aid. The IMD will use the same calculation algorithm to determine the amount of amplification; however, the hearing thresholds will be transferred directly to the software after the automated hearing screening. The same default settings will be applied, and the HCP will save the fitting. The hearing aids will be fit exactly the same electro-acoustically. The main difference is that the IMD is more patient driven; therefore, there could be a psychological effect that results in a higher rating for one hearing aid or the other.

In summary, the primary reason for this study is to evaluate the new self-directed hearing aid fitting software. It will not replace the current software but supplement markets that may not have the infrastructure or the trained personnel to use the current software. Or in markets that currently use the standard software, it could be used as an optional fitting method for other outlets beside the clinics where the standard software is used, such as a pharmacy. The goal is to evaluate the audiological performance, possible narrative effect, and safety of the new software before it's released to the market.

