### 5.2 Secondary Outcomes

The secondary outcome variables are the audiometry as measured with the standard test and with the automated system. The data analysis will focus on the hearing threshold differences with both procedures in a nested model: ear-participant-investigator.

Additionally data logging from the hearing aids will be recorded as an indication of hearing aid use. The data will be averaged from each ear. The following data will be used:

1. Daily usage in hours per day,

2. Acoustical environment in percentage for the following listening environments: quiet, speech in quiet, speech in noise, and noise.

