### 11.1 Hypothesis

Both devices will have the same electro-acoustical performance; however, it is suspected that changing the fitting procedure might influence the subjective benefit for the hearing aid user. Research suggests that placebo effect might impact hearing aid trials (Dawes et al., 2013) and that clinician behavior might also modify the perceived benefit of hearing aids (Naylor et al., 2015). The designed test will investigate the potential effect of the IMD compared to the RMD on first time users.

The test should answer the following research questions:

- Narrative effect of fitting procedure: Do different fitting procedures lead to differences in perceived benefit with hearing aids despite similar electro-acoustical performance? (Questionnaires)
- 2. Self-administrated audiometry: Is AMTAS self-administrated screening equivalent to standard clinical procedure? (hearing loss thresholds)

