#### 11.4.3 Secondary Analyses

The standard audiological hearing test results will be compared to those completed with the automated IMD hearing screening. Data analysis will focus on hearing threshold differences with both procedures in a nested model: ear-participant-investigator.

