1.1 Research question

The test should answer following research questions:

- 1. Narrative effect of fitting procedure: are different fitting procedures leading to differences in perceived benefit with hearing aids despite similar electro-acoustical performances? (Questionnaires)
- 2. Self-administrated audiometry: is AMTAS self-administrated audiometry equivalent to standard clinical procedure? (hearing loss thresholds)

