2.2 Secondary outcomes

2.2.1 Audiometry

AMTAS is a self-administrated audiometry procedure that have shown equivalence to manual audiometry (Elkeboom et al., 2013). Across all tested audiometrical frequencies (250 up to 8000 kHz), the mean difference between both procedures (self-administrated vs. manual) was about 0.1 dB HL (min = -3 dB HL at 250 Hz and max = 3.6 dB HL at 8000 Hz). Data analysis will focus on hearing threshold differences with both procedures in a nested model: ear-participant-investigator.

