4.1 Analysis methods

Linear mixed effect regression will be used on the IOI-HA questionnaire, chi2 distribution on the preference test and paired t-test on audiometrical thresholds. Principal component analysis will be made on different outcomes and explanatory variables combinations.

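### Research question 2 asks whether the self-test is equivalent to standard audiometry, but neither the paired t-test nor the nested model has a margin, interval criterion or reading rule, and the two analyses are not reconciled

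*Protocol*

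**What the plan says.** Both documents list the same second research question. Protocol 11.1 puts it as "Is AMTAS self-administrated screening equivalent to standard clinical procedure"; SAP 1.1 as "is AMTAS self-administrated audiometry equivalent to standard clinical procedure". In each, hearing thresholds are the data that should answer it. Protocol 3.1 gives the purpose: "Audiometry will be compared to ensure that similar results are achieved with the IMD as those from a standard audiometry test".

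Two analyses of these thresholds are named.

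- Protocol 11.4 names "a paired t-test on hearing thresholds", and SAP 4.1 names "paired t-test on audiometrical thresholds".
- Protocol 11.4.3 says "Data analysis will focus on hearing threshold differences with both procedures in a nested model: ear-participant-investigator". Protocol 5.2 and SAP 2.2.1 say the same.

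The comparison is a secondary outcome: "The secondary outcome variables are the audiometry as measured with the standard test and with the automated system". The synopsis and Protocol 6.1 call the study exploratory, while Protocol 4.1 also describes it as the last validation before the product goes on sale.

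The background figures come from a cited validation study of the automated method. Protocol 3.4 gives a between-method SD of 6.4 dB across frequencies and mentions 5 dB as an acceptable test-retest difference in standard audiometry. SAP 2.2.1 gives a mean difference of about 0.1 dB over all frequencies, ranging from -3 dB at 250 Hz to 3.6 dB at 8000 Hz, and introduces the method with "AMTAS is a self-administrated audiometry procedure that have shown equivalence to manual audiometry". Neither document adopts any of these figures as a criterion for this trial.

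**The concern.** A paired t-test asks whether the mean difference is zero. An equivalence question asks whether the difference is small enough not to matter, and that cannot be answered until someone says what small enough is. A precise trial can find a trivial offset significant, and an imprecise one can miss an offset that matters. The nested model can supply an estimate, but it too has no rule for reading it, and nothing says whether frequency is a factor, is averaged over or is analysed separately.

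This is the only planned direct comparison of the self-test with standard audiometry. Protocol 8.1.2 and 8.2.1 state that both fittings use the self-test thresholds. That keeps the IMD-RMD comparison fair, but it also means that this contrast cannot isolate a screening error, since the error would be present in both periods. If the threshold comparison has no agreed reading, a conclusion that the screening is equivalent would have no basis fixed in advance.

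**Working it through.** **Power stated in the plan.** The documents' power figures concern the preference question only. They reproduce from a noncentral chi-squared with noncentrality n·w²:

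- w = 0.65, 2 df, n = 24: 24 × 0.4225 = 10.14, power 0.821 (stated 0.82).
- w = 0.6, 1 df, n = 24: 24 × 0.36 = 8.64, power 0.836 (stated 0.84).

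No power, margin or precision target is given for thresholds, so what follows is illustration.

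**Inputs.** SD of differences 6.4 dB (Protocol 3.4), assumed to hold at a single frequency. One difference per participant. n = 24 and 40 (synopsis). Offsets of 3 and 3.6 dB, the sizes reported at 250 and 8000 Hz (SAP 2.2.1). A limit of 5 dB, borrowed from the test-retest remark in Protocol 3.4 and not proposed as a margin.

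**Where the two questions part.** Standard error = SD/√n. The t-test is significant when |mean| > t(0.975)·SE. The 90% interval lies inside ±5 dB when |mean| < 5 − t(0.95)·SE. If the observed SD equals 6.4:

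| n | SE | significant if the mean exceeds | 90% interval inside ±5 if the mean is below |
|---|---|---|---|
| 24 | 1.306 | 2.069 × 1.306 = 2.70 | 5 − 1.714 × 1.306 = 2.76 |
| 40 | 1.012 | 2.023 × 1.012 = 2.05 | 5 − 1.685 × 1.012 = 3.3 |

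At n = 40, any observed mean between about 2.05 and 3.3 dB is both significantly different from zero and within the illustrative limit. At n = 24 that band is narrow at this SD, and it widens or closes as the observed SD varies.

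**Probability that the t-test is significant** (noncentral t, two-sided 0.05, noncentrality = offset/SE):

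| true offset | n = 24 | n = 40 |
|---|---|---|
| 3 dB | 0.595 | 0.824 |
| 3.6 dB | 0.751 | 0.934 |

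A 3.6 dB offset, below 5 dB, is thus declared a difference in 75% or 93% of trials. A 3 dB offset goes undetected in 1 − 0.595 = 40% of trials at n = 24 and 1 − 0.824 = 18% at n = 40. Whether either offset matters is exactly what the plan leaves undecided.

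**Probability of significant and 90% interval inside ±5 dB, true offset 3 dB** (integrating over the sampling distribution of the SD):

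- One value per participant: 10% at n = 24, 44% at n = 40.
- Mean of two ears at an assumed between-ear correlation of 0.5, so SD = 6.4 × √(1.5/2) = 5.54: 26% and 64%.

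**Probability that the 90% interval lies inside ±5 dB** (n = 24, one value per participant): 96% at a 0.1 dB offset, 44% at 3 dB, 27% at 3.6 dB.

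**Frequency.** If thresholds were pooled over frequency, offsets of opposite sign could cancel. The cited study shows the pattern: about 0.1 dB overall, with -3 and 3.6 dB at the extremes. The documents do not say that they will be pooled.

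**The case against.** The best defence is that audiometry is a secondary outcome of an exploratory study, that no power is claimed for it, and that the nested model is said to be the focus and can yield an estimate. All of that is true. It limits the seriousness of the point, but it does not supply a way to read the result, and the question is still worded as one of equivalence that the trial should answer.

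Four stronger readings are tempting, and the documents do not support them.

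- *Equivalence will be declared from a non-significant test.* Neither document says so; the gap is that no reading is stated.
- *Non-significance would often hide an unacceptable offset.* At the one documented SD, a true 5 dB offset is missed only about 4% of the time at n = 24 and 0.2% at n = 40. Given a non-significant test at n = 24 and a true offset of 3 or 3.6 dB, the 90% interval reaches beyond 5 dB in 17% or 24% of cases with one value per participant. With two ears at correlation 0.5 this falls to about 4% to 7%, and those true offsets are inside 5 dB anyway.
- *No other measurement could expose a faulty screening.* The unaided-versus-aided speech tests (Protocol 9.2.3) and the questions on loud sounds, discomfort and feedback (Protocol 9.2.4) could show a gross error. What they lack is a comparison against standard thresholds.
- *Frequency offsets will be averaged away.* That is a risk only if frequencies are pooled, which is unstated.

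**Conclusion.** The point holds. The plan poses an equivalence question, names a test that cannot answer it, names a second model for the same data without ranking the two, and gives neither one a margin, interval criterion or reading rule. It should be fixed, at a level that suits an exploratory secondary outcome.

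The percentages rest on the cited 6.4 dB SD applying at one frequency, on one value per participant unless two ears are stated, and on 5 dB as an illustration; a different limit would change them. The mismatch itself depends on none of these. A reader might infer that the IMD-RMD comparison is biased. It is not, because both fittings use the same thresholds.

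**What to change.** In Protocol 11.4 and 11.4.3 and SAP 4.1, make the nested model of IMD-minus-standard threshold differences the lead analysis, with frequency as a fixed factor and ear within participant within investigator. Report the estimate and confidence interval for each frequency. State that a non-significant test will not be read as equivalence.

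- *Main option.* Reword question 2 in Protocol 11.1 and SAP 1.1 as estimation of the difference, and leave equivalence out of the conclusion. With SD 6.4 dB and one value per participant, the 95% half-width is about 2.7 dB at n = 24 and 2.05 dB at n = 40, so the estimates would be informative.
- *Alternative.* Keep the equivalence wording only with a margin that the sponsor justifies and fixes before database lock, and a 90% interval rule applied at each frequency.

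The cost is wording and a little more analysis; no new data are needed. Under a margin rule, equivalence may not be shown at some frequencies: with the illustrative 5 dB margin at n = 24, power is 44% at a 3 dB offset and 27% at 3.6 dB. The estimation option avoids this.

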#### 11.4.1 Datasets to be analysed, analysis populations

Analysis population: a single group that had the same treatment (per protocol set).

The included subjects are first time hearing aid users with the same hearing aid model across the population. As hearing loss does not normally fluctuate, we assume that their hearing capabilities are stable over time and that the performance with a hearing aid can be compared over a longer period without any wash out period. Subjects' individual auditory capacities (hearing loss degree, noise tolerance, speech recognition) vary, however the sample is considered as a homogenous population regarding their experience with the RMD. It will be ensured that the acceptance to generic amplification via hearing aids is not tested but an actual evaluation of the difference between the RMD and the IMD. A single assignment treatment will be considered representative of clinical intervention, i.e. when an experienced hearing aid user acquires a new device.

#### 11.4.2 Primary Analysis

The narrative effect on the subject perception of the end user will be measured using a standardized questionnaire, the IOI-HA, and a custom product questionnaire. The questionnaires will be administered twice during the study, once after each field trial period. The responses for the IMD will be compared with those for the RMD. At the last visit the subjects will complete a preference questionnaire based on the Naylor et al. (2015).

#### 11.4.3 Secondary Analyses

The standard audiological hearing test results will be compared to those completed with the automated IMD hearing screening. Data analysis will focus on hearing threshold differences with both procedures in a nested model: ear-participant-investigator.

#### 11.4.4 Explan atory analyses

Speech intelligibility will be measured using the Freiburger Sprachverständnistest. The level at which 50% of words are correctly repeated will be recorded as test outcomes by the investigator for the unaided and aided conditions for each test session.

The differences between unaided and aided (for IMD and RMD) speech intelligibility will be compared and used as an explanatory variable for the model.

The subjects' perceived hearing handicap will be measured with a standardized questionnaire. Participants that are not often affected in their daily life by their hearing impairment, might report smaller benefit from amplification with a hearing aid. Understanding and quantifying their struggles with the principal component analysis could be used to improve the modelling of the results.

The usage of hearing aids will be recorded as another indication of hearing aid use. The data will be averaged from each ear. The following data will be used:

- 1. Daily usage in hours per day,
- Acoustical environment in percentage for following listening environments: quiet, speech in quiet, speech in noise, and noise

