#### 4.3 Secondary Objectives

Secondary objectives are to assess the performance of the hearing aids after being programmed by both fitting methods. The hearing aids will be the same electro-acoustically and should provide equivalent aided benefit.

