### 5.3 Other Outcomes of Interest

Explanatory variables include speech intelligibility testing using a multi-syllable word test called the Freiburger Sprachverständnistest (FST). This test will measure the objective benefit (difference from unaided and aided) from the hearing aids as fitted with the RMD and the IMD. Also the perceived handicap associated with hearing impairment may influence the perceived benefit from the hearing aids. The Gothenburg Profile (GP) will be used to quantify perceived handicap and the influence it may have on the primary outcome. A custom packaging questionnaire specific to hearing aids will test the usability of the packaging.

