# 6. STUDY DESIGN

### 6.1 General study design and justification of design

This is a controlled, randomized, open label, cross-over, comparative clinical investigation conducted at two sites within Canton Bern, Switzerland.

The exploratory study is based on a population of hearing impaired people that have hearing loss appropriate for the hearing aids.

As a control, the RMD will be used to fit the hearing aids as well as the IMD. Additionally, a control situation will be implemented by using an unaided test condition in laboratory speech testing.

There is no placebo or "fake" device that does not provide amplification. A randomized cross-over design will be used with one group using the device programmed with the RMD first and the other using the device programmed with the IMD and then switching. The testing will be unblinded as the subjects can clearly see a difference between fitting methods. Although two hearing tests will be completed (standard audiometry and IMD screening), the hearing aids will be programmed only with the IMD screening results in order to reduce variability in the analysis of the results. Therefore, the hearing aids will be acoustically programmed the same, but this will not be explained to the participants.

The same randomized test order will be used to test in a simulated environment. At the end of the field test period the participants will return to the clinic. They will be given a speech test in the unaided condition and the aided condition with the hearing aids as they have worn them for the previous 10 days. They will then be fit with the other method (whichever they did not have in the first round), and then have speech testing again in the aided and unaided condition at the end of the field test period.

The participants will be expected to participate for approximately 1 month for a combination of field tests and lab tests. For lab tests they will not spend more than 1.5 hours in the clinic for testing. They will be expected to come for 3 visits in total. Field trial periods will not last more than 10 +/-5 days.

The sequence will begin with the screening visit which will also be the first intervention visit if they satisfy the inclusion criteria and if they choose to join the study. The entire test procedure will be explained, and they will be given a Patient Informed consent form to read which will need to be signed, dated, and returned before any trial procedures begin.

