2.3 Explanatory variables

2.3.1 Speech intelligibility Freiburger Test

The freiburger sprachtest is a standardized speech test in German speaking areas. Percentages of correctly repeated words are recorded as test outcomes by the investigator for the unaided and aided conditions for each test session.

Differences between unaided and aided (IMD vs. RMD) at 50% speech intelligibility will be used as an explanatory variable for the model.

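### The speech comparison in Protocol 11.4.4 subtracts a fresh unaided score at each visit with weight fixed at 1; adjusting for that score would usually be more precise at little cost

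*Protocol*

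**What the plan says.** Protocol 6.1 has participants tested unaided and aided after the first field period, and then says they will "have speech testing again in the aided and unaided condition at the end of the field test period". Protocol 11.4.4 confirms that the 50% levels "will be recorded as test outcomes by the investigator for the unaided and aided conditions for each test session", so each completer has two unaided and two aided levels. The same section continues: "The differences between unaided and aided (for IMD and RMD) speech intelligibility will be compared", and it gives these differences a second role as an explanatory variable. Protocol 5.3 gives the purpose: "This test will measure the objective benefit (difference from unaided and aided) from the hearing aids as fitted with the RMD and the IMD".

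SAP 2.3.1 gives the score only the explanatory role: "Differences between unaided and aided (IMD vs. RMD) at 50% speech intelligibility will be used as an explanatory variable for the model". The methods lists in Protocol 11.4 and SAP 4.1 name a mixed model for the IOI-HA, a chi-squared test for preference and a paired t-test for thresholds. Neither names a method for the speech comparison.

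Two further statements matter. Protocol 11.4.1 says of the participants: "we assume that their hearing capabilities are stable over time". Protocol 4.3 sets the secondary objective: "The hearing aids will be the same electro-acoustically and should provide equivalent aided benefit". Protocol 5.3 and 11.4.4 treat speech as an other or explanatory outcome; only the synopsis lists it among the secondary endpoints.

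**The concern.** In a within-person comparison the unaided level is the same underlying quantity in both periods: no aid is worn, so the fitting method cannot change it, and hearing is assumed stable. The balanced cross-over is relied on for average period or learning effects (SAP section 1). Subtracting a newly measured unaided level at each visit therefore does not correct the IMD-RMD difference for the person's true level, which cancels anyway. It adds two measurement errors, and it removes whatever error the two tests in a session share. Which effect is larger depends on how strongly those errors are correlated, and the plan fixes the weight at 1 without knowing this.

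At stake is the width of the interval around the speech contrast, the objective evidence bearing on 4.3. Equivalent benefit is expected there and no margin is given, so a needlessly wide interval is easily read as showing no difference.

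**Working it through.** **The plan's own figure.** The Protocol's only power figure (11.2) is for the preference test: w = 0.65, 2 df, N = 24, alpha 0.05. The noncentrality is 24 × 0.65² = 10.14, which gives power 0.821; the stated 0.82 reproduces. It says nothing about speech, for which the documents give no SD, test-retest error, correlation or power.

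**Inputs.** From the documents: one unaided level (U) and one aided level (A) per session, two sessions, stable true hearing, and a minimum of 24 participants. Assumed: each measurement varies around the person's stable level with variance s², equal for U and A; errors are independent between sessions; U and A errors within a session have correlation r. Because r is unknown, a range is shown.

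**Variances per participant.** Let D_A = A_IMD − A_RMD and D_U = U_IMD − U_RMD. Each has variance 2s², and their covariance is 2rs².

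- Planned contrast: (U−A)_IMD − (U−A)_RMD = D_U − D_A, with variance 2s² + 2s² − 4rs² = 4s²(1−r).
- Unadjusted aided contrast: D_A, with variance 2s².
- Adjusted aided contrast: D_A given D_U, with variance 2s²(1−r²).

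The mean of D_U does not depend on fitting method, so apart from sign all three estimate the same effect.

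**Planned against unadjusted.** The ratio is 2(1−r): 2.00 at r=0, 1.50 at 0.25, 1.00 at 0.5, 0.50 at 0.75. Simulation gave 1.997, 1.500, 0.999 and 0.500.

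**Adjusted against planned.** With a known slope the ratio is 2(1−r²) / [4(1−r)] = (1+r)/2. Estimating the slope costs something at N = 24. With two sequence means fitted, 22 degrees of freedom remain for the spread of D_U, and the expected inflation is 1 + 1/(22−2) = 1.05. The ratio becomes 1.05(1+r)/2.

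| r | Planned (÷s²) | Adjusted, slope estimated (÷s²) | Change in variance |
|---|---|---|---|
| 0 | 4.00 | 2.10 | −47.5% |
| 0.3 | 2.80 | 1.91 | −31.8% |
| 0.5 | 2.00 | 1.575 | −21.3% |
| 0.7 | 1.20 | 1.071 | −10.8% |
| 0.9 | 0.40 | 0.399 | −0.3% |
| 0.95 | 0.20 | 0.205 | +2.4% |

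Break-even is at 1.05(1+r)/2 = 1, or r = 0.905. Simulated trials of 24 participants, with period fitted, agreed: savings of 48%, 32%, 21 to 22%, 11% and 0 to 1%, then a loss of 2 to 3%.

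**Unequal variances.** If the unaided variance is k times the aided, planned against unadjusted is 1 + k − 2r√k. At r=0 that is 1.5 for k = 0.5 and 3.0 for k = 2; break-even is r = √k/2.

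**How the covariate enters.** The adjusted variance requires the within-person slope. If the raw unaided level is entered with only a random participant intercept, the slope mixes in the between-person association. In a simulation assuming between-person SD 10, error SD 2, between-person slope 1, residual between-person SD 1 and r=0, the variance was 3.76s² against 3.94s² for the planned contrast, so almost all of the saving was lost.

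**The case against.** The strongest reply is that same-session subtraction is worthwhile. Attention, practice or calibration on the day affects both tests, and subtracting one from the other removes it. That stands: at r=0.7 the planned variance is 1.20s² against 2.00s² for an unadjusted aided comparison. A reader might infer that the unaided score adds only noise, or that the plan doubles the variance. The documents support neither. Doubling relative to the unadjusted contrast requires r=0 with equal variances, and the stable-hearing assumption concerns hearing loss, not session error. Nor does it follow that the unaided test should be dropped: it defines objective benefit in 5.3, and the adjusted analysis needs it.

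Second, benefit is the construct named in 5.3 and 4.3, and the score has a planned explanatory role. This also stands as a limit on the remedy, which must leave those uses intact.

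Third, the Protocol says only that the differences will be compared, so the exact contrast is partly inferred. It is the natural reading, and the lack of a named method is itself a reason to specify one.

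Fourth, the study is exploratory and speech is mostly placed below the secondary outcomes. That lowers the importance without removing the point.

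**Conclusion.** The point holds as a precision improvement. Fixing the unaided weight at 1 is less efficient than letting the data set it unless r is above about 0.9. At N = 24 the variance saving runs from about 48% (r=0) through 21 to 22% (r=0.5) to nothing (r=0.9), with a loss of 2 to 3% at 0.95. These figures rest on equal error variances, independent sessions and stable hearing; r and s² are not in the documents, so no single value can be claimed.

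A reader might go further and conclude that the planned contrast is biased, or that objective 4.3 cannot be addressed. Neither follows: the contrast targets the right effect, and only its precision is affected. The lack of an equivalence margin is a separate gap that this change does not close.

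**What to change.** In Protocol 11.4.4 and SAP 2.3.1 and 4.1:

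- Estimate the IMD minus RMD difference in the aided 50% level, in dB, with a 95% CI. Adjust for period and for the unaided level centred on each person's mean. Equivalently, regress the within-person aided difference on the within-person unaided difference and sequence (coded ±1), and read the effect at an unaided difference of zero.
- State that the raw unaided level is not to be entered with only a random intercept.
- Keep unaided-minus-aided benefit for description, and for its planned use as an explanatory variable and in the principal component analysis.
- Reconcile what is recorded: Protocol 11.4.4 records the level giving 50% correct, while SAP 2.3.1 first describes percentages correct. The analysis above needs the level.

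The cost is a few sentences and one degree of freedom, with a slight loss of precision if r is very near 1. No extra visit, test or participant is needed.
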